6.9 Follow-up assessments

This visit will be conducted by phone 30 days post the week 96 visit (+/- 7 day window). The following evaluations are to be performed:

- Symptoms review and adverse events
- Urine home pregnancy test for WOCBP. The result should be communicated via a telephone call visit and recorded in the patient records and in the eCRF.

A follow-up visit is not required if a patient withdraws from IMP prior to week 96. In this case, an early termination visit should be conducted instead. See section 6.10.

6.10 Early Termination visit

In the case of early termination, every attempt will be made to ensure the subject has a termination visit. At this visit, the following evaluations and procedures are to be performed:

- Symptoms review and adverse events
- Alcohol intake, smoking habit and recreational drug use
- Total cholesterol and lipids (HDL, LDL and triglycerides) (fasted)

CONFIDENTIAL

- PBMC (Required unless exemption documented in site contract i.e. if site does not have capacity to process).
- Blood sampling for measurement of DTG & RPV (PK assessment). (Pre- or post-dose (as appropriate) at early termination visit and/or in the event of virological failure (see section 6.18). A post dose sample will be taken within 20-28 hours.
- Vital signs (pulse, blood pressure: after 10 minutes resting)
- Physical examination (symptom-directed)
- Weight
- Review of concomitant medications
- Laboratory evaluations: haematology and biochemistry (fasting) (Appendix 1)
- HIV RNA viral load
 - Note: In event of viral load failure follow section 6.18 viral failure & resistance assessment procedures.
- CD4 & CD8 count / %
- EuroQoL questionnaire
- Pittsburgh sleep questionnaire
- Patient treatment satisfaction questionnaire
- DDI assessment
- Adherence assessment (including date/time of last dose on PK days including ETV visit and/or in the event of virological failure)
- Pregnancy test for WOCBP (β -HCG).

Patients will be requested to attend for remaining visits and complete study assessments to week 96 even if they are no longer taking study medication.

See Appendix 1 for details of assessments.

6.11 Qualitative assessments – Nested studies

This section is not applicable

Subjects may continue study drug for Grade 1 or 2 allergic reactions at the discretion of the Investigator. The subject should be advised to contact the Investigator immediately if there is any worsening of symptoms or if further systemic signs or symptoms develop. Antihistamines, topical corticosteroids, or antipruritic agents may be prescribed.

Subjects with Grade ≥ 3 allergic reactions that are considered to be possibly or probably related to the investigational product(s) should permanently discontinue the investigational product regimen and the subject should be withdrawn from the study. Subjects should be treated as clinically appropriate and followed until resolution of the adverse event.

Subjects in the CAR arm who are receiving ABC as part of their NRTI background regimen should be evaluated for the possibility of a clinically suspected ABC hypersensitivity reaction (HSR) and managed appropriately as outlined in the local prescribing information for ABC.

Rash

Mild to moderate rash is an expected adverse reaction for both DTG and RPV containing ART. Episodes generally occur within the first ten weeks of treatment, rarely require interruptions or discontinuations of therapy and tend to resolve within two to three weeks. The index case of hypersensitivity with DTG involved a profuse, purpuric and coalescing leukocytoclastic vasculitis as well as clinically significant liver chemistry elevations. Other than this case, no other instances of serious skin reaction, including Stevens - Johnson syndrome (SJS), Toxic Epidermal Necrolysis (TEN) and erythema multiform, have been reported for DTG, RPV or DTG/RPV FDC in clinical trials.

Subjects with an isolated Grade 1 rash may continue study drug at the Investigator's discretion. The subject should be advised to contact the Investigator immediately if there is any worsening of the rash, if any systemic signs or symptoms worsen, or if mucosal involvement develops.

CONFIDENTIAL

Subjects may continue study drug for an isolated Grade 2 rash. However, study drug (and all other concurrent medication(s) suspected in the Investigators causality assessment) should be permanently discontinued for any Grade ≥ 2 rash that is associated with an increase in ALT. The subject should be advised to contact the physician immediately if rash fails to resolve (after more than two weeks), if there is any worsening of the rash, if any systemic signs or allergic symptoms develop, or if mucosal involvement develops.

Subjects should permanently discontinue study drug (and all other concurrent medication(s) suspected in the Investigators causality assessment) for an isolated Grade 3 or 4 rash, and the subject should be withdrawn from the study. Subjects should be treated as clinically appropriate and followed until resolution of the AE.

The rash and any associated symptoms should be reported as adverse events (see section 8) and appropriate toxicity ratings should be used to grade the events (based on DAIDS toxicity gradings).

If the etiology of the rash can be definitely diagnosed as being unrelated to IP and due to a specific medical event or a concomitant non-study medication, routine management should be performed and documentation of the diagnosis provided.

Subjects in the CAR arm who are receiving ABC as part of their NRTI background regimen should be evaluated for the possibility of a clinically suspected ABC hypersensitivity reaction (HSR) and managed appropriately as outlined in the local prescribing information for ABC.

Subjects withdrawing from the trial may be replaced if considered necessary by the Chief investigator.

6.13 Liver Chemistry Stopping and Follow up Criteria

Liver chemistry threshold stopping criteria have been designed to assure subject safety and to evaluate liver event etiology during administration of study drug and the follow-up period. Study drug must be stopped if any of the following liver chemistry criteria are met:

- ALT $\geq 3 \times \text{ULN}$ and bilirubin $\geq 2 \times \text{ULN}$ (>35% direct bilirubin; bilirubin fractionation required)

NOTE: serum bilirubin fractionation should be performed if testing is available. If testing is unavailable, record presence of detectable urinary bilirubin on dipstick, indicating

CONFIDENTIAL

direct bilirubin elevations and suggesting liver injury. If testing is unavailable and a subject meets the criterion of total bilirubin ≥ 2 xULN, then the event meets liver stopping criteria and should be reported as an SAE. If INR is obtained, include values on the SAE form. INR elevations >1.5 suggest severe liver injury.

- ALT ≥ 8 xULN;
- ALT ≥ 3 xULN (if baseline ALT is $<$ ULN) with symptoms or worsening of acute hepatitis or hypersensitivity such as fatigue, nausea, vomiting, right upper quadrant pain or tenderness, fever, rash, or eosinophilia, OR;
- ALT ≥ 3 x baseline ALT with symptoms or worsening of acute hepatitis or hypersensitivity such as fatigue, nausea, vomiting, right upper quadrant pain or tenderness, fever, rash, or eosinophilia;
- ALT ≥ 5 xULN and < 8 xULN that persists > 2 weeks (with bilirubin < 2 xULN and no signs or symptoms of acute hepatitis or hypersensitivity);
- ALT ≥ 5 xULN but < 8 xULN and cannot be monitored weekly for > 2 weeks;

Subjects who develop ALT ≥ 5 xULN should be followed weekly until resolution or stabilisation (ALT < 5 xULN on 2 consecutive evaluations).

When liver chemistry stopping criterion is met, the following procedures must be followed:

- **Immediately** hold dolutegravir and rilpivirine. If a causal relationship between the liver event and dolutegravir and rilpivirine cannot be ruled out, then dolutegravir and rilpivirine must be permanently discontinued and the Subject not rechallenged due to the risk of a recurrent reaction. If the liver event has a clear underlying alternative cause, other than drug-induced liver injury, then Drug Restart may be considered (see below).
- Report the event to the study sponsor pharmacovigilance team within 24 hours of learning its occurrence (see section 8.3)
- Events of possible drug-induced liver injury (DILI) with hyperbilirubinemia defined as ALT ≥ 3 xULN and bilirubin ≥ 2 xULN ($> 35\%$ direct) will be reported to the Sponsor as SAEs using the SAE reporting form Complete the liver event CRF for all events meeting liver stopping criteria.

CONFIDENTIAL

- Perform liver event follow up assessments (described below), and monitor the subject until liver chemistries resolve, stabilise, or return to baseline values as described below;
- Make every reasonable attempt to have subjects return to clinic within 24 hours for repeat liver chemistries, liver event follow up assessments (see below), and close monitoring;
- A specialist or hepatology consultation is recommended;
- Monitor subjects twice weekly until liver chemistries (ALT, AST, alkaline phosphatase, bilirubin) resolve, stabilise or return to within baseline values;

Consider the following additional tests to further evaluate the liver event:

- Viral hepatitis serology including:
 - Hepatitis A IgM antibody;
 - HBsAg and Hepatitis B Core Antibody (IgM);
 - Hepatitis C RNA;
 - Hepatitis E IgM antibody;
- Cytomegalovirus IgM antibody;
- Epstein-Barr viral capsid antigen IgM antibody (or if unavailable, obtain heterophile antibody or monospot testing);
- Syphilis screening
- Drugs of abuse screen including alcohol
- Serum acetaminophen test (APAP adduct test)
- Serum creatine phosphokinase (CPK) and lactate dehydrogenase (LDH);
- Fractionate bilirubin, if total bilirubin is greater than 1.5xULN;
- Obtain complete blood count with differential to assess eosinophilia;
- Anti-nuclear antibody, anti-smooth muscle antibody, and Type 1 anti-liver kidney microsomal antibodies;
- Liver imaging (ultrasound, magnetic resonance, or computerised tomography) to evaluate liver disease;

CONFIDENTIAL

- Record the appearance or worsening of clinical symptoms of hepatitis, or hypersensitivity, fatigue, decreased appetite, nausea, vomiting, abdominal pain, jaundice, fever, or rash as relevant on the AE report form;
- Record use of concomitant medications, acetaminophen, herbal remedies, other over the counter medications, or putative hepatotoxins, on the concomitant medications report form.

Restarting Study Drug

If a causal relationship between the liver event and DTG/RPV FDC cannot be ruled out, then DTG/RPV FDC must be permanently discontinued and the Subject not rechallenged.

Drug Restart Following Transient Resolving Liver Events Not Related to Study Drug

Restart can be considered when liver chemistries improve to within 1.5x baseline and ALT<3xULN) where:

- Liver chemistries have a **clear underlying cause** other than drug-induced liver injury (e.g. biliary, pancreatic events, hypotension, acute viral hepatitis). Furthermore, there should be no evidence of alcoholic hepatitis or hypersensitivity, and the drug should not be associated with HLA markers of liver injury.
- The subject is receiving compelling benefit and benefit of drug restart exceeds risk
- Approval from the Chief Investigator plus Ethics Committee/IRB & ViiV Healthcare (as appropriate) for the drug restart has been obtained.
- The subject has been provided with a clear description of the possible benefits and risks of drug restart, including the possibility of recurrent, more severe liver injury or death.
- The subject has also provided signed informed consent specifically for the restart. Documentation of informed consent must be recorded in the study file.
- Following drug restart, the Subject will return to the clinic once a week for liver chemistry tests for one month or for as long as clinically indicated and then laboratory monitoring may resume as per protocol. If protocol defined stopping criteria for liver chemistry elevations are met, study drug must be stopped.

6.14 Suicidal Risk Monitoring

Subjects with HIV infection may occasionally present with symptoms of depression and/or suicidality (suicidal ideation or behaviour). In addition, there have been some reports of depression, suicidal ideation

CONFIDENTIAL

and behaviour (particularly in patients with a pre-existing history of depression or psychiatric illness) in some patients being treated with integrase inhibitors, including DTG. Therefore, it is appropriate to monitor subjects for suicidality before and during treatment.

Subjects should be monitored appropriately and observed closely for suicidal ideation and behaviour or any other unusual changes in behaviour. It is recommended that the investigator consider mental health consultation or referral for subjects who experience signs of suicidal ideation or behaviour.

See section 8 for reporting details.

6.15 Decline in Renal Function

Subjects who experience an increase in creatinine from Baseline of 45 mMol/L (or 0.5 mg/dL) without associated evidence for proteinuria should return for a confirmatory assessment within 2 to 4 weeks. A urinalysis and urine microalbumin/creatinine ratio should be done at this confirmatory visit. If the creatinine increase is confirmed, the investigator should contact the sponsor to discuss additional follow-up and medical management.

Subjects who have a decline in creatinine clearance of >50% must return for a confirmatory assessment as soon as possible. A urinalysis and urine microalbumin/creatinine ratio should be done at this confirmatory visit. If the estimated creatinine clearance has declined by >50% (confirmed), then study medication should be withheld and the investigator should contact the sponsor to discuss the rationale for restarting study drugs (if appropriate). Consideration for confounding factors (e.g. NRTI background therapy, other medications, dehydration, concurrent conditions) should be taken into account, and a nephrology consult may be obtained. If a subject in the control group is also receiving TDF, then a switch to an alternative fully active NRTI should be considered if restarting study medication. Current local prescribing information should be consulted for additional details on dosing background therapy in renally impaired subjects. If study medication is reinitiated, it should have been withheld for no more than 4 weeks. If IP is not reinitiated the subject must be withdrawn.

Proximal Renal Tubule Dysfunction (PRTD) is defined as:

- Confirmed rise in serum creatinine of ≥ 0.5 mg/dL from baseline AND serum phosphate < 2.0 mg/dL;
- Either of the above accompanied by any two of the following:

CONFIDENTIAL

- Glycosuria (≥ 250 mg/dL) in a non-diabetic;
- Low serum potassium (< 3 mEq/L);
- Low serum bicarbonate (< 19 mEq/L).

Subjects meeting criteria for PRTD must return for a confirmatory assessment within 2 weeks. A urinalysis should be done at the time of the confirmatory assessment. If PRTD is confirmed the drugs should be terminated and the sponsor should be contacted to discuss the rationale for restarting study drugs (if appropriate). If a subject is also receiving TDF/FTC, then a switch to an alternative NRTI combination should be considered if restarting study medication. If re initiation of study medication is planned, study medication should be withheld for no more than 4 weeks. Subjects on ABC/3TC FDC may switch to the individual components dose adjusted for renal dysfunction according to approved prescribing information, or switch to alternative nucleosides at the discretion of the Investigator.

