6.16 Proteinuria

Subjects with an abnormal urine microalbumin/creatinine ratio (> 0.3 mg/mg, > 300 mg/g or > 34 mg/mmol) that represents a change from baseline and no associated increase in creatinine, should have a repeat spot urine microalbumin/creatinine ratio performed within 2-4 weeks. If confirmed, then consideration should be made for additional evaluation after consultation with the sponsor. Additional evaluation may include a creatinine measurement and nephrology referral.

Subjects with an abnormal urine albumin/creatinine ratio (> 0.3 mg/mg, 300 mg/g or > 34 mg/mmol and representing a change from baseline) and a serum creatinine increase > 45 mMol/L (or 0.5 mg/dL) should have confirmation of both results within 2 weeks. If confirmed, the study sponsor should be immediately contacted. Agreement on further management should be agreed between the investigator and study sponsor.

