8.2 Operational definitions for (S) AEs

An adverse event is any untoward medical occurrence in a subject administered a pharmaceutical product and which does not necessarily have a causal relationship with the study treatments. An adverse event (AE) can therefore be any unfavourable and unintended sign (including an abnormal laboratory finding), symptom, or disease temporally associated with the use of a medicinal (investigational) product, whether or

CONFIDENTIAL

not considered related to the medicinal (investigational) product.

Adverse events observed by the Investigator, or reported by the subject, and any remedial action taken, will be recorded in the subject's CRF and should be verifiable in the subject's notes throughout the study. The nature of each event, time of onset after drug administration, duration and severity will be documented together with the Investigator's opinion of the causal relationship to the investigational product (unrelated, unlikely, possible, probable, and definite).

All subjects experiencing adverse events, whether considered associated with the use of the study medication or not, must be monitored until the symptoms subside and any clinically relevant changes in laboratory values have returned to baseline, or until there is a satisfactory explanation for the changes observed.

Procedures such as surgery should not be reported as adverse events. However, the medical condition for which the procedure was performed should be reported if it meets the definition of an adverse event. For example, an acute appendicitis that begins during the adverse event reporting period should be reported as the adverse event and the resulting appendectomy noted on the CRF.

Planned procedures such as surgery pre planned prior to the subject's enrolment into the study do not need to be reported as adverse events if these are documented as planned at the screening visit.

Clinically significant changes in physical examination and blood safety profiles should also be recorded as adverse events.

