9.4 Adjusted analysis

The primary efficacy analysis will be by multiple logistic regression. This analysis will be adjusted for two baseline categorical variables which might influence the 48-week outcome: presence of M184V mutation at baseline and CD4 count at baseline (above versus below 350 cells/UI).

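### The creatinine-rise trigger in Protocol 6.15 and 6.16 is printed in two units that disagree about 1000-fold; millimoles should almost certainly be micromoles

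*Protocol*

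**What the plan says.** Protocol 6.15 sets a first-level renal trigger. A participant with "an increase in creatinine from Baseline of 45 mMol/L (or 0.5 mg/dL") and no accompanying proteinuria returns for confirmation within 2 to 4 weeks, and a confirmed rise leads to contact with the sponsor. Protocol 6.16 repeats the threshold for participants who also have an abnormal urine albumin/creatinine ratio: "a serum creatinine increase > 45 mMol/L (or 0.5 mg/dL"). There, both results are to be confirmed within 2 weeks and the sponsor contacted at once if they are.

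Three other rules bear on the point:

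- The definition of proximal renal tubule dysfunction (PRTD) in 6.15 gives the rise in mass units only: "Confirmed rise in serum creatinine of ≥ 0.5 mg/dL from baseline".
- The clearance rule in 6.15 is a percentage: "Subjects who have a decline in creatinine clearance of >50% must return for a confirmatory assessment".
- Section 6.16 gives the urine ratio cut-off in two units, "> 300 mg/g or > 34 mg/mmol", which supplies a creatinine conversion from within the protocol.

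No section restates the trigger in micromol/L or corrects it.

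**The concern.** In both sentences the word joining the two values presents them as the same threshold in different units. Serum creatinine is commonly reported in either mg/dL or micromol/L, and a rise of 45 in millimoles per litre looked out by the factor of 1000 that separates milli from micro.

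The risk table in Protocol 1.1 notes mild creatinine elevations with dolutegravir and names 6.15 and 6.16 as the mitigation, so this trigger is likely to be looked up. Under 6.18, creatinine is measured in local laboratories, and the sites are in seven European countries. If some of those laboratories report in SI units (an assumption; the documents do not say), those sites would turn to the molar figure, which is the wrong one. The protocol gives no correct SI value anywhere else. At stake is a missed confirmatory test or a missed call to the sponsor.

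**Working it through.** **Inputs, all from the protocol**

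- Trigger: 45 mMol/L, equated with 0.5 mg/dL (6.15 and 6.16).
- Urine ratio cut-off: 300 mg/g, equated with 34 mg/mmol (6.16).

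**Step 1. Creatinine mass per mmol.** The urine ratio is albumin per unit of creatinine, so dividing its two forms cancels the albumin:

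34 mg/mmol ÷ 300 mg/g = 0.1133 g/mmol = 113.3 mg creatinine per mmol.

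If 34 is rounded from anything between 33.5 and 34.5, the range is 111.7 to 115.0 mg per mmol.

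**Step 2. Try to reproduce the stated equivalence.** Use mmol/L = (mg/dL × 10) ÷ (mg per mmol):

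0.5 mg/dL = 5 mg/L; 5 ÷ 113.3 = 0.0441 mmol/L = 44.1 micromol/L (range 43.5 to 44.8).

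The printed 45 mMol/L is not reproduced.

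**Step 3. Convert the printed molar value back.**

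45 mmol/L × 113.3 mg/mmol = 5100 mg/L = 510 mg/dL (range 502.5 to 517.5).

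510 ÷ 0.5 = 1020 (range 1005 to 1035).

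**Step 4. Test the obvious repair.**

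45 micromol/L = 0.045 mmol/L; 0.045 × 113.3 = 5.10 mg/L = 0.51 mg/dL (range 0.503 to 0.518).

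This agrees with the printed 0.5 mg/dL after rounding.

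| Reading of the molar value | In mg/dL | Against the printed 0.5 mg/dL |
|---|---|---|
| 45 mmol/L (as printed) | 510 | about 1020 times too high |
| 45 micromol/L | 0.51 | agrees |

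As a cross-check, assuming a creatinine molar mass of 113.12 g/mol (not given in the documents), 0.5 mg/dL is 44.2 micromol/L and the factor is 1018.

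**The case against.** The strongest objection is that the plan may not contain the error at all. A micro sign can turn into an m when a PDF is converted to text. Section 6.16 spells true millimole in lower case and then prints mMol in its creatinine rule, which would fit a lost micro sign. The other place in the Protocol that needs a micro sign, the CD4 unit in 9.4, prints as "above versus below 350 cells/UI", so the Protocol text offers no example of a micro sign that survived.

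Against this, a Greek beta survives in the Protocol (6.7), the trigger is printed identically in two sections, and the Protocol is loose with units elsewhere, for example the capital M in copies/ML in 9.2.2. The SAP does print a mu in the CD4 unit (6.4.2), but that is a different document and counts for little. Identical print in two places is also weak evidence, since a conversion fault can repeat as easily as a typing error can be copied. The text alone cannot settle the matter. A real error is at least as plausible as an artefact, and this objection stands as a condition on the finding.

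The second objection is that the error would do little harm, and it largely holds. The correct mg/dL figure sits beside the wrong one each time, and a rise of 510 mg/dL is not physiologically possible, so few readers would apply it literally. Neither affected step stops treatment. The clearance rule, which withholds drug once the fall is confirmed, and the PRTD rule, "If PRTD is confirmed the drugs should be terminated", do not use the molar value. Section 8.2 is a further backstop: "Clinically significant changes in physical examination and blood safety profiles should also be recorded as adverse events".

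**Conclusion.** As printed, the two forms of the creatinine-rise trigger disagree by a factor of about 1020 (1005 to 1035), in two sentences of the protocol, and nothing elsewhere corrects them. The arithmetic rests only on the protocol's own conversion. Whether the fault is in the plan or in the conversion from PDF is open, so confidence that it is a real error is medium.

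Severity is minor. This is an inconsistent unit in a working safety threshold, which the adjacent mg/dL value keeps usable. At most a repeat test or a sponsor contact could be missed. Design, eligibility, sample size, power and the primary analysis are unaffected.

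**What to change.** Look at the two sentences in the source file. If they show a micro sign, nothing needs changing. If they show millimoles, replace the unit in 6.15 and 6.16 so that each gives 45 micromol/L (or 0.5 mg/dL), and tell sites by clarification letter or in the next amendment. The cost is one unit corrected in two sentences, with no change to design or analysis.
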